5.10.2. UICC Reminder Contacts

Subjects who provide consent and contact information but do not complete Survey #1, will be contacted by email, letter and/or phone after 7 days as a reminder that their survey is not complete. A maximum of 6 reminder contacts will be made. Enrolling sites will be asked to provide subject contact information to the UICC if the subject has not provided it (or it was not valid) in the study website (Steps 3 and 4) to enable these reminder contacts.

5.10.3. Follow-up surveys

Approximately six months after subjects complete the first survey, the UICC will send invitations for subjects to complete the 6-month survey via email (for study website enrollees) or mail (for mail enrollees). Content for this and the remaining follow-up surveys (at 12 and 18 months) are similar to the Survey #1 (baseline), except they do not include questions about chronic conditions, demographics, thoughts on cancer diagnoses and treatment decisions, or health literacy.

If the subject has not completed the 6-month survey within 7 days of the invitation, a reminder email, mail, or phone invitation will be sent/made. These reminders will be automated by the UICC or PHR, as applicable. This process will be repeated (every 7 days) for a maximum of six contacts until the subject completes the survey or declines to complete it. Identical invitation and nonresponse procedures will be implemented for the 12- and 18-month surveys. (See Appendix C for details on pre- and post-consent contacts.)

If the UICC is unsuccessful at contacting subjects using the information provided by the subject (e.g., data entered erroneously on the PHR), the UICC will communicate with the enrolling site to review the patient medical record to attempt to find and share updated contact information with the UICC.

Subjects will be able to access their study accounts (PHR website) at least through the end of 2025. A UICC research team member or the PHR will be used to send automated reminders to patients for

subsequent completion of the 6-, 12- and 18-month follow-up questionnaires (calculated from the date of their baseline questionnaire completion).

5.10.4. Subject Compensation

Regardless of the enrollment means, subjects will be compensated \$40 for completing Survey #1, and \$20 for completing each subsequent survey (i.e.: Surveys #2-4), for a total of \$100.00. Checks will be sent by the UICC to the address provided by the subject on their PHR registration page or mailed questionnaire (using personal data collected post consent).

5.11. Post-enrollment monitoring

The UICC will record all subject contacts and status updates and will share this information as needed with enrolling sites.

In some cases, it may be necessary for an enrolling site or the UICC to confirm the identities of enrolled persons and/or to confirm that the linkage between person and assigned credentials is correct. Information collected from subjects post-enrollment may be shared between a site and the UICC to resolve any such discrepancies.

5.12. Population of CDM PCORnet_TRIAL table

UICC will provide guidance to sites on populating the PCORnet_TRIAL table. This is necessary as the outcomes query provided to sites will reference this table. Sites will need to populate the table prior to running the outcomes query. The UICC will share a list of all persons who enrolled in the study as a check against site records to confirm that the PCORnet_TRIAL table is populated correctly at all sites.

5.13. Data Crosswalks

As illustrated in Figure 3, it is necessary to establish and maintain the following data crosswalks to ensure the integrity of data linkages across sources:

Responsible party	Linkage of...	To...	Notes
UICC	PARTICIPANTID	Study Website Credentials	UICC will establish this linkage and maintain it in the study database (SQL)
Sites	PARTICIPANTID and Study Website Credentials	CDM PATID	Establish linkage in REDCap as eligible patients are identified from your source EMR data. UICC to provide PARTICIPANTID and Study Website Credentials
Sites	CDM PATID	MRN or similar ID	Sites should already have a way to link CDM PATID to MRN or similar ID that can be used to directly identify patients. This will be needed for chart review activities.

[figure not shown]

Figure 3: NET-PRO study enrollment workflow

6. DATA SOURCES

The data sources for NET-PRO will include:

- 1) EMR data
 - Clinical and billing data from the PCORnet CDM
 - Abstracted medical record data (per chart review)
- 2) Patient surveys (Baseline, 6, 12, and 18 month follow-up)
- 3) Patient study website navigation data

6.1. EMR data – Clinical and billing data from the PCORnet CDM

The PCORnet CDM is a key component of the PCORnet Distributed Research Network infrastructure, and will serve as the primary data source for the NET-PRO study. In late 2023, the UICC will request data from sites on all enrolled subjects. Data will include demographics, toxicity outcomes, vitals and vital status, treatments, laboratory tests and results, health conditions (comorbidities), tumor characteristics (from tumor registry variables/tumor tables in the CDM), disease status, and encrypted IDs used to link patient care across sites. The data will cover the period two years prior to the subject's NET diagnosis through approximately 36 months after the date they joined the study. Note, as per the inclusion criteria, we will not be excluding patients who do not have 2 years of look-back data prior to their diagnosis date. Table 2 summarizes the variables that will be obtained from the CDM. The specific code lists for derivation of these variables in the CDM will be later specified and distributed to sites.

Table 2: Patient, clinical and tumor variables that will be measured from the CDM

Concept/variable		CDM Tables
Demographics	Date of birth, sex, Hispanic, Race	Demographic Table
Toxicity outcomes	Acute renal failure, dialysis, liver failure	Diagnosis Table
Vitals	Height, weight, systolic and diastolic blood pressure, smoking	Vitals Table
Cancer Treatments	Somatostatin Analogues (SSAs) (octreotide, lanreotide, pasireotide) Bevacizumab, Cytotoxic chemotherapy, Everolimus, Interferon alpha, Hepatic Artery Bland-, Chemo- or radioembolization, PRRT -Lutetium Lu-177 dotatate, PRRT-Yttrium-90 Dotatoc, Small molecule TKIs, Telotristat ethyl)	Dispensing, prescribing, procedures, and medications administered Tables
Lab values	Alanine transaminase (ALT), Albumin and Microalbumin Albumin/Creatinine and Microalbumin/creatinine Ratio, Alkaline phosphatase (ALP), Aspartate transaminase (AST), AST/ALT ratio, Blood Urea Nitrogen, Chromogranin A, Cystatin C, Hemoglobin, Ki-67, Lymphocytes, Pancreastatin, Serum or Blood Creatinine, Somatostatin, Total Bilirubin	Lab results
Comorbid conditions	Chronic Pulmonary Disease, Congestive Heart Failure, Coronary Artery Disease, Diabetes with complications, Diabetes without complications, Hypertension, End Stage Renal Disease, Mild Liver Disease, Severe Liver Disease, Peripheral vascular disease, Renal Disease, Myocardial Infarction	Diagnosis Table, Conditions Table (for conditions in the 2 years prior to GEP-NET/lung NET diagnosis)
Vital status	Vital status (death date, cause of death)	Death Table. Death Cause Table – supplemented with local site linkages and patient survey data

Linkage	Patient ID, token	Hash token table (Datavant link module)
Tumor Characteristics	Tumor characteristics (NAACCR required variable list (i.e.: tumor grade, stage, nodal status and other relevant pathological characteristics))	Tumor Table or cancer registry data sources

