4. STUDY DESIGN

4.1. Time anchors for study cohort

Study Period: 01/01/2019 to 12/31/2023 (5 years, max 60 months follow-up)

Index Date: Date of diagnosis of eligible NET tumor in the study period

Source Data Range: 01/01/2017-12/31/2023 (7 years, includes 2-year look-back period)

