6.2. EMR data – Abstracted medical record data (per chart review)

Targeted chart reviews will be conducted at one point in time (towards the end of study follow-up period i.e.: Dec 2023) for all subjects enrolled in NET-PRO. Chart reviews will be undertaken to evaluate the following items:

- 1) Disease status (four-category variable defined below)
- 2) Clinical variables found to be insufficiently populated in the CDM
- 3) Other Clinical/pathological characteristics not recorded elsewhere (examples below)

The UICC has budgeted \$100 for chart abstraction for each case. In consultation with the clinician group, the consensus was that application of the RECIST criteria may be impracticable given current NET-PRO resources. Targeted chart abstraction will include a four-level categorization of disease status:

- 1) Disease control
- 2) Progression (no change in treatment)
- 3) Progression (with changes in treatment)
- 4) Indeterminate.

It was agreed that the clinical assessment and plan, would be the best source for identification of disease status for chart abstractors.

Other variables that may be selected for targeted chart review include clinical variables found to be insufficiently populated in the CDM. These may include interval lab values related to serum creatinine, BUN and eGFR (related to ascertainment of kidney toxicity for Aim 3) before and after PRRT cycles. It will also be important to collect tumor variables (i.e.: stage, grade, nodal status) for patients who were not identified from institutional tumor registries. An additional target for chart review may be other prognostic clinical/pathological characteristics not recorded elsewhere in the CDM or cancer registry data sources. For example information on mitotic count, chromogranin A (CgA) and Ki-67 proliferation index.

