- 3) **Progression-free survival (PFS).** Time to event data will be calculated from the index date (date of diagnosis) to the earliest of disease progression, death from any cause or end of study follow-up (12/31/2023). Acknowledging that patients may have more than one progression over the study period endpoints of median time to first progression (time from initiation of first-line therapy to progression) and time to second progression (time from second-line therapy initiation to progression) will be observed from targeted chart reviews at annual intervals. In collaboration with our clinician group we have discussed the various limitations of the application of the RECIST 1.1 criteria in NETs. These limitations include an overemphasis on tumor progression (given the low proliferation rate of GEP-NETs, monitoring changes in tumor size is suboptimal), and RECIST 1.1 criteria do not reflect overall tumor load or response to therapy in metastatic patients (i.e.: issues with clinical significance of radiologic progressions). Optimizing the management of NET patients therefore requires considering clinical, biological, and pathological aspects of the tumor. We have therefore chosen to categorize disease progression as DISEASE CONTROL (complete or partial response & stable disease), PROGRESSION (with no treatment change), PROGRESSION (with treatment change), and INDETERMINATE. This clinician-anchored approach has been found to be an optimal and valid method (versus RECIST1.1) for evaluating real-world tumor burden endpoints from EMR data [55].
[Time Frame: median time to progression, assessed annually via chart review]
- 4) **Overall Survival (OS).** Time to event data will be calculated from the date of diagnosis (index date) to the date of death from any cause, or end of study follow-up (12/31/2023). Death and vital status (death date, cause of death) will be pulled from the death table, and death cause table in the CDM. This data may be supplemented from site linkage to the social security death index or cancer registry sources (where possible). Given the prospective nature of the study we also have potential for passive surveillance/follow-up with participant/next of kin with information collected on our follow-up questionnaires.
[Time Frame: Up to 5 years]

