B22	Data linkage plan	Develop a data linkage plan that corresponds with PCORnet Common Data Linkage, if available, in collaboration with the dataset owner(s).	1/1/2022	12/31/2021	
B23	100% of the IRB approvals across sites submitted to PCORI	Update IRB information in PCORI Online	1/1/2022		5/31/2022
B	Report Submission	Submit Interim Progress Report to PCORI via the PCORI Online system accessed through: https://pcori.force.com/engagement	1/1/2022	12/29/2021	
C1	Finalize comparators for Aims 2 & 3	The collection of HRQoL information from Aim 1 will be available for a decent sample of NET patients at this time. Information from Aim 1 will be used – with input from the Patient Advocacy Committee (PAC) and Clinician Group – to finalize the comparators for Aims 2 and 3.	2/28/2022		5/31/2022

Milestone - Deliverable ID	Milestone - Deliverable Name	Description	Due Date	Completion date	Projected Completion Date
C2	Patient enrollment (25%)	25% of participants (N = 753) screened, enrolled, and consented to the study.	3/1/2022		6/30/2022
C3	Validate Study Preliminary Results	Complete validation of sample of events. (Number and type of events will be distributed across the participating CRNs to assure appropriate representation.) Provide a summary of preliminary results of the validation study in interim progress report.	5/1/2022		
C4	Presentation to PCORnet Steering Committee	Annual presentation to PCORnet Steering Committee on progress of study, lessons learned, and recommendations for improvement of PCORnet infrastructure	7/1/2022		
C	Report Submission	Submit Interim Progress Report to PCORI via the PCORI Online system accessed through: https://pcori.force.com/engagement	7/1/2022		
D1	Finalize and submit copy of revised study protocol in PCORI Online.	Refer to the PCORI Methodology Standards for required elements of the study protocol.	7/1/2022		
D2	NET PHR portal finalized	Design parameters and feedback from NET patient sessions is incorporated into the NET PHR, tested, and ready for deployment for existing and future enrollees	7/1/2022		
D3	Submit IRB Continuing approval	Submit IRB approval of revised study protocol via the PCORI Online system.	7/1/2022		

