D4	Programmatic evaluation materials due to PCORI.	Submit document that demonstrates study progress and feasibility based on metrics provided by PCORI to awardee. PCORI initiates Programmatic Evaluation. Metrics will include: the validity of cohort identification and its size and characteristic; feasibility of recruitment; generalizability of the sample; feasibility of data linkages (if relevant); validity and completeness of study outcomes; suggestions of needed enhancements or revisions to study protocol, as well as associated timeline. PCORI will provide recommendations about proceeding to next steps of the study within 45 days.	7/1/2022		
D5	Patient enrollment (50%)	50% of participants (N = 1505) screened, enrolled, and consented to the study.	10/1/2022		
D	Report Submission	Submit Interim Progress Report to PCORI via the PCORI Online system accessed through: https://pcori.force.com/engagement	1/1/2023		
E1	Patient enrollment (75%)	75% of participants (N =2258) screened, enrolled, and consented to the study.	6/1/2023		
E2	Submit IRB Continuing approval	Submit IRB approval of revised study protocol via the PCORI Online system.	7/1/2023		
E3	Presentation to PCORnet Steering Committee	Annual presentation to PCORnet Steering Committee on progress of study, lessons learned, and recommendations for improvement of PCORnet infrastructure	7/1/2023		
E	Report Submission	Submit Interim Progress Report to PCORI via the PCORI Online system accessed through: https://pcori.force.com/engagement	7/1/2023		
F1	Develop dissemination plan for rare disease tools and resources	Submit dissemination plan to PCORI via PCORI Online system	1/1/2024		
F	Report Submission	Submit Interim Progress Report to PCORI via the PCORI Online system accessed through: https://pcori.force.com/engagement	1/1/2024		
G1	Patient enrollment (100%)	100% of participants (N = 3010) screened, enrolled, and consented to the study.	2/1/2024		

Milestone - Deliverable ID	Milestone - Deliverable Name	Description	Due Date	Completion date	Projected Completion Date
G2	Submit IRB Continuing approval	Submit IRB approval of revised study protocol via the PCORI Online system.	6/30/2024		
G3	Completion of Data Collection for All Study Aims	Awardee must ensure that all data collection for all study aims as specified in the research plan is completed	6/30/2024		

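### EMR data ending in December 2023 cannot cover the stated 36 months after joining; on the projected timeline about 75% of subjects cannot have even 18 months

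*Protocol*

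**What the plan says.** Section 6.1 names the PCORnet CDM as the primary data source, supplying treatments, laboratory values and toxicity codes. On timing it says "In late 2023, the UICC will request data from sites on all enrolled subjects", with coverage from two years before diagnosis "through approximately 36 months after the date they joined the study". No later refresh is described.

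The other time anchors are:

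- Section 4.1: "Source Data Range: 01/01/2017-12/31/2023".
- Section 6.2: one chart review per subject, "towards the end of study follow-up period i.e.: Dec 2023".
- Section 7.2: PFS and OS follow-up closes on 12/31/2023.
- Section 11, Table 8: first patient (B12) due 9/30/2021, now projected for 4/29/2022.
- Table 8, C2: "25% of participants (N = 753) screened, enrolled, and consented to the study", due 3/1/2022, now projected for 6/30/2022.
- Table 8, D5 and E1: 1505 due 10/1/2022 and 2258 due 6/1/2023.
- Table 8, G1: "100% of participants (N = 3010) screened, enrolled, and consented to the study", due 2/1/2024.
- Table 8, G3 and G4: data collection and analysis for all aims complete by 6/30/2024.

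**The concern.** Section 6.1 counts its 36 months from the date of joining, but enrolment was projected to start only 20 months before the data end and to finish after it. The coverage figure and the extraction date cannot both be right.

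What is at stake is the link between surveys and records. HRQoL is measured at 0, 6, 12 and 18 months from the baseline survey and is to be related to treatment regimen. If EMR data stop in December 2023, later surveys from most subjects will have no EMR treatment, laboratory or progression data alongside them. Table 4 also lists the Aim 3 renal outcome at 0, 6, 12 and 18 months. If month 0 means enrolment, its later points are cut short in the same way.

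**Working it through.** **Method.** Longest follow-up after joining = data end minus first enrolment. Share with at least *k* months = cumulative enrolment at (data end minus *k* months), divided by 3010. Enrolment is interpolated linearly between the Table 8 milestones.

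**Inputs that reproduce.** 14 sites × 215 = 3010. 25% of 3010 = 752.5, given as 753. 01/01/2019 to 12/31/2023 is the stated 60 months from diagnosis.

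**The stated 36 months does not reproduce.**

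- 4/29/2022 to 12/31/2023 = 20.1 months.
- 9/30/2021 (original first-patient date) to 12/31/2023 = 27.0 months.
- 4/29/2022 to 6/30/2024 = 26.1 months.
- 9/30/2021 to 6/30/2024 = 33.0 months.

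With data to 12/31/2023, 36 months would require joining by 12/31/2020, before the project began.

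**Share with *k* months after joining, data to 12/31/2023, projected milestones.**

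- 18 months: join by 6/30/2022, which is the projected C2 date. 753/3010 = 25.0% can; 2257/3010 = 75.0% cannot. No interpolation is needed.
- 12 months: join by 12/31/2022. 1505 + 753 × 91/243 = 1787, or 59.4%.
- 6 months: join by 6/30/2023. 2258 + 752 × 29/245 = 2347, or 78.0%.
- Enrolled after the data end: 3010 − (2258 + 752 × 213/245) = 98, or 3.3%.

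**Sensitivity of the 18-month figure.**

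| Milestones | Data end | Cannot have 18 months |
|---|---|---|
| Projected | 10/1/2023 | 100% |
| Projected | 12/1/2023 | 86.7% |
| Projected | 12/31/2023 | 75.0% |
| Original due dates | 12/31/2023 | 60.9% |
| Either | 6/30/2024 | 40.7% |

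Original due dates: 753 + 752 × 121/214 = 1178 joined by 6/30/2022, so 39.1% can. Data to 6/30/2024: 1505 + 753 × 90/243 = 1784 joined by 12/30/2022, so 59.3% can.

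**The case against.** Four points on the other side have force.

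**Anchor.** The index date is diagnosis, from 2019 onward, and EMR data reach back two years before it. Treatment sequencing, PFS and OS are all timed from diagnosis. If diagnoses were uniform over 2019–2023 (an assumption), 42/60 = 70% would have at least 18 months from diagnosis. A reader might infer that three quarters of the cohort lack 18 months of EMR follow-up altogether. The documents do not support that; the 75% applies only to time after joining.

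**Renal outcome.** A reader might infer that Aim 3 loses its power. That is not shown. Section 7.1 times creatinine around PRRT cycles, and Table 4 does not tie month 0 to enrolment. Counting only subjects with an 18-month value (25% of 300 = 75) and setting this against the protocol's 180 mixes bases, because 180 is 60% of 300 for survey response. It also ignores the mixed models of Section 9.1, which use partial series. Suppose month 0 were enrolment and 300 PRRT patients were observed to 0, 6, 12 and 18 months at 97, 78, 59 and 25%. A large-sample 3-df test of losses of 2, 4 and 6 then has about 91% power (lag-1 correlation) to 99% (constant correlation) at SD 15. Starting from 180 patients it has about 70% to 90%. At the protocol's main SD of 5, power stays near 100%.

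**Survey treatment data.** Table 3 collects self-reported treatment at every follow-up survey, so late HRQoL scores are not without treatment information. This does not replace creatinine or progression data.

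**Surveys may also stop.** If G3 closes surveys on 6/30/2024, the 40.7% who join too late for 18 months by then have no 18-month survey to pair. The EMR cut-off would then account for 75.0 − 40.7 = 34.3 percentage points. Section 5.10.3 keeps portal access through 2025, so whether surveys stop then is unclear.

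None of these rescues the 36-month statement.

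**Conclusion.** The contradiction stands. No enrolment schedule or cut-off in the protocol yields 36 months of EMR data after joining; the current dates allow about 20. About 75% of subjects cannot have 18 months after joining, and about 3% would enrol after the data end.

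The 20-month maximum and the 75% rest on the projected dates for first patient and 25% enrolment and on data running to 12/31/2023. The 75% falls to 61% on the original due dates and rises if the pull comes earlier in late 2023. The 6- and 12-month shares and the 3% also assume linear accrual between milestones.

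The shortfall bears on EMR treatment, laboratory and progression data paired with the 6-, 12- and 18-month surveys, and on the Aim 3 renal time points only if month 0 is enrolment. Diagnosis-timed PFS, OS and sequencing are not undermined, and no quantified loss of Aim 3 power is established.

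**What to change.** 1. Reconcile Sections 4.1, 6.1, 6.2 and 7.2 with Table 8, so that there is one data-end date and it does not fall before enrolment closes.
2. Run the final CDM query and the one chart review as late as the 6/30/2024 data-collection milestone allows, and use that extraction date for administrative censoring. Waiting for the last 18-month survey is not compatible with Table 8: a subject joining on 2/1/2024 reaches 18 months in about August 2025.
3. Replace the 36 months with the achievable maximum: about 20 months with data to 12/31/2023, or about 26 with data to 6/30/2024.
4. State the numbers expected to have 12 and 18 months of EMR data after joining: 1787 and 753 with data to 12/31/2023, or 2347 and 1784 with data to 6/30/2024.
5. Say what month 0 is for the Aim 3 renal outcome.

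The cost is a later run of a query already planned, a later date for the chart review already budgeted per case, and amended wording. That wording includes the 60-month maximum, which would become up to 66 months from diagnosis with data to 6/30/2024. G4 puts completion of analysis on the same day as G3, so the later the extraction, the less time is left for analysis unless G4 also moves. If the dates cannot move, items 3 to 5 need wording only.
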